5.3.6 Vital Signs

Vital signs will be measured as outlined in Table 1 with the patient in a sitting position after 5 minutes' rest and will include pulse rate, SBP, and DBP. Body temperature will be measured at Screening Visit 1 according to local standard-of-care.

5.3.7 Physical Examination, Including Height and Body Weight

Patients will undergo complete physical examination or symptoms-directed physical examinations as outlined in Table 1.

The complete physical examination will include assessments of the standard physical examination items, including general appearance, skin, eyes, ears, nose, throat, head and neck, heart, chest and lungs, abdomen, extremities, lymph nodes, musculoskeletal, neurological, and other body systems, if applicable, for describing the status of the patient's health.

Body weight and height (height at Screening Visit only) will also be measured and recorded. The patient should be dressed in light clothing, without shoes.

Investigators should pay special attention to clinical signs related to previous serious illnesses. Any new abnormalities or worsening of existing abnormalities that are associated with signs and/or symptoms (except for SCCHN related -pre-existing- conditions, including disease progression) should be reported as AEs or SAEs, as appropriate (see Section 7).

5.4 Pharmacokinetics

Blood samples will be collected for measurement of plasma concentrations of setanaxib and its metabolite GKT138184 for all patients during the study at the visits specified in Table 1. The PK blood volumes to be collected during the study will be provided in the ICF and/or in the central laboratory manual.

PK samples will be collected just before the start of pembrolizumab infusion and before the IMP morning dose at Day 1, Week 3, Week 24, Week 51, and Week 105, and anytime for the PK samples taken on the day of the second biopsy and at EoT Visit.

Instructions for the collection and handling of biological samples will be provided by the sponsor (or designee) and will be included in the central laboratory manual. The actual date and time that each sample is collected will be recorded.

The measurement of plasma setanaxib and GKT138184 concentrations will be performed by a central laboratory.

6 TREATMENTS

6.1 Investigational Medicinal Product

6.1.1 Description of Investigational Medicinal Product

Test Product	
IMP/non-IMP:	IMP
Name:	Setanaxib
Dose:	800 mg BID (2 tablets in the morning and 2 tablets in the evening) Setanaxib tablets will contain 400 mg setanaxib powder formulated with excipients.
Mode of administration:	Orally (or via either a feeding tube or a percutaneous endoscopic gastrostomy device in case patients are unable to swallow tablets)
Manufacturer:	Aptuit [name]
Placebo	
Substance:	Matching placebo tablets, containing only excipients, will be provided. The placebo tablets will be visually identical to setanaxib tablets to maintain the blind.
Dose:	Not applicable
Mode of administration:	Orally (or via either a feeding tube or a percutaneous endoscopic gastrostomy device in case patients are unable to swallow tablets)
Manufacturer:	Aptuit [name]

6.1.2 Preparation, Handling, and Storage

Refer to the pharmacy manual for full details regarding the preparation of setanaxib and placebo tablets.

The investigator (or designee) is responsible for the safe and proper storage of IMP at the site. The bottles containing setanaxib and placebo tablets will be stored under controlled conditions according to the storage requirements described on the label. The IMP is to be

stored at room temperature (15-25°C). The tablets must not be frozen or stored above 25°C or 77°F. The investigator (or designee) will instruct the patients to store the IMP in accordance to the instructions on the label.

6.1.3 Labelling and Shipment

Setanaxib and placebo bottles will be labelled in accordance with all applicable regulatory requirements and Good Manufacturing Practice guidelines.

Setanaxib and placebo will be provided in high-density polyethylene (HDPE) bottles containing:

- Setanaxib 400 mg tablets
- Matching placebo tablets

Each bottle will contain 70 tablets.

The labelling of the placebo will be the same as the test product to maintain the blind.

Setanaxib and placebo will be shipped and stored under controlled conditions according to the storage requirements. The IMP is to be stored and shipped at room temperature (15-25°C).

Refer to the pharmacy manual for full details for labelling and shipment of the IMP.

An authorised service provider will label the IMP bottles and will supply the IMP to local depots/study sites on behalf of the sponsor (or designee).

6.2 Blinding

The study is double-blinded. The investigator, the site personnel, the sponsor and their representatives involved in monitoring and conducting the study, and the patients will be blinded to treatment assignments.

Randomisation data will be kept strictly confidential, accessible only to authorised staff and the IDMC until the time of unblinding. Authorised staff may include the randomisation statistician, who will store the master randomisation list in a secure system, an unblinded statistician, and unblinded programmers, who will provide the IDMC with unblinded safety data for review, and as and when required, in accordance with the procedures described in the IDMC Charter. All authorised unblinded staff must be documented.

The setanaxib and placebo tablets are visually identical to maintain the blind. Setanaxib and placebo bottles will be coded and labelled in a manner that protects blinding. The

coding system will permit rapid identification of the product (in case of medical emergencies), that does not permit undetectable breaking of the blind.

Breaking of the blind is only allowed in the case of an emergency, when knowledge of the IMP is essential for the clinical management of the patient. In such emergency situations, the responsibility to break the treatment code resides solely with the investigator. The investigator will have immediate access to break the blind through the interactive response technology (IRT). The investigator must contact the sponsor within 1 working day after the event, without revealing to the sponsor (or contract research organisation [CRO]) the results of the code break, except to the designated global patient safety representative. The investigator must document the date of unblinding and the reason.

Emergency unblinding will be organised through IRT. The investigator must record the date of unblinding and the reason. All breaks of the blind must be adequately documented.

If an SAE is reported, the designated global patient safety representative may unblind the treatment assignment for the individual patient through IRT to meet regulatory reporting requirements.

6.3 Method of Assigning Treatment

Each patient will have a unique patient screening number obtained from the IRT. This will be assigned at the Screening Visit. If a patient is rescreened (see Section 4.3), the rescreened patient should be assigned a new unique screening number. The investigator will keep a record (the patient screening log) of patients who entered Screening.

Once the patient has been successfully screened and the investigator has determined that the patient is eligible, the patient will be confirmed as enrolled within the IRT.

Randomisation will be performed via a centralised IRT. On Day 1, eligible patients will be assigned to setanaxib or placebo in a 1:1 ratio, stratified by HPV status. Each patient will receive a unique randomisation number when he/she is assigned treatment. Patients will be allocated to treatment according to the randomisation code.

The randomisation codes will be prepared by the randomisation statistician. The randomisation statistician will store the master randomisation list in a secure system.

If a patient withdraws from study participation, his/her unique identification number(s) cannot be re-used for another patient.

6.4 Dose and Administration

At each dispensing visit, patients will receive setanaxib or placebo bottles. Each bottle contains 70 tablets. Patients will be dispensed 1 to 3 IMP bottles at each dispensing visit, as described in the site operations manual, to ensure that the patient has sufficient IMP to last until the next scheduled visit.

Patients will take 4 tablets per day. Two tablets will be taken in the morning and 2 tablets will be taken in the evening.

- Patients allocated to setanaxib 800 mg BID will self-administer 2 tablets of setanaxib 400 mg in the morning and 2 tablets of setanaxib 400 mg in the evening.
- Patients allocated to placebo will self-administer 2 placebo tablets in the morning and 2 placebo tablets in the evening.

Patients will be instructed not to take their morning IMP dose on PK visit days until after the study assessments have been completed, except the PK visit days where tumour biopsy is collected and the EoT Visit.

Patients should take the first dose at the clinic under supervision of site staff to ensure the first dose is taken and that patients can swallow the tablets. The first dose taken should be documented in medical records.

For patients that can swallow setanaxib/placebo tablets, the tablets should be taken orally with food or up to 30 minutes after a meal. Each tablet should be taken separately and swallowed with water. The patients will be instructed to distribute their morning and evening doses as evenly as possible.

Patients who cannot swallow tablets and have either a feeding tube or a percutaneous endoscopic gastrostomy (PEG) device inserted are allowed to disperse setanaxib tablets in water using a compatible syringe and administer the dispersed tablets through the feeding device. See further details in the pharmacy manual. A separate patient information leaflet should be provided to the patient and verbal instructions given by the investigator or other appropriately trained staff at the clinic on how to disperse and administer the IMP.

Patients will be provided with a patient IMP dosing card. Patients will be instructed to record the date and time of each dose that they take, as well as the route of administration (oral, feeding tube, or PEG device), on the dosing card straight after they have taken the tablet.

Patients will be reminded to bring the IMP (including any empty bottles) and the patient IMP dosing card with them to each study visit.

The IMP dosing card will be considered as a source document. Site personnel will record the date and time of the IMP dose as well as the route of administration (oral, feeding tube, or PEG device) prior to PK Visits (ie, prior to the PK sample) in the eCRF.

6.4.1 Dose Modification

Dose interruptions are required in case of anaemia and hypothyroidism, when the events meet the criteria as defined in Section 5.3.2.1, and Section 5.3.2.2, respectively. Events that require permanent discontinuation of IMP are listed in Section 4.3.1.

Dose reduction of setanaxib to 400 mg BID to manage anaemia, hypothyroidism, or any Grade 3 or otherwise intolerable toxicity, which is considered related to setanaxib may be instituted at the investigator's discretion after discussion with the medical monitor.

6.4.2 Dechallenge and Rechallenge

Investigational medicinal product should be interrupted in cases of anaemia (as described in Section 5.3.2.1) or hypothyroidism (as described in Section 5.3.2.2). If the criteria specified in those sections are met, IMP may be resumed. If the rechallenge results in the IMP interruption criteria being met again, the IMP must be permanently discontinued (see Section 4.3.1).

6.4.3 Intervention After the End of the Study

Continued access to IMP is not planned beyond the completion of the study.

6.5 Precautions and/or Lifestyle Considerations

There are no other lifestyle considerations (such as dietary or physical activity restrictions) for this study further to those listed in the inclusion/exclusion criteria (Section 4).

6.6 **Prior Medication**

See Section 4 for details of the prior medication that is permitted or prohibited according to the inclusion and exclusion criteria.

The following medications are prohibited:

- Anti-cancer mAb treatment within 4 weeks prior to study Day 1
- Chemotherapy, targeted small molecule therapy or radiation therapy within 2 weeks prior to study Day 1 (radiation therapy can be allowed for palliative therapy of bone metastasis only)

- Treatment with any investigational agent within 12 weeks of Screening Visit 1 or 5 half-lives of the IMP (if known), whichever is longer
- Current enrolment in another interventional clinical study
- Medications known to be potent CYP3A4 inhibitors or inducers, as well as potent UGT1A9 inhibitors or inducers, within 21 days prior to IMP administration

Live-attenuated vaccines should be avoided where possible within 30 days before study treatment but may be used where other alternatives are not available, considered inferior, or otherwise unsuitable.

6.7 Background Treatment

Setanaxib or matching placebo will be administered in combination with pembrolizumab.

Pembrolizumab (KEYTRUDA, Merck) is a PD-1-blocking antibody indicated for the first-line treatment of patients with metastatic or unresectable recurrent SCCHN. Pembrolizumab is administered as 200-mg IV infusion q3w. Treatment will be initiated on Day 1, ie, at the same time as the first dose of IMP.

Pembrolizumab is considered as a non-investigational product and will be administered according to current clinical guidelines and labelling.

Refer to the pharmacy manual for full details for labelling and shipment of pembrolizumab.

6.8 Concomitant Medication

See Section 4 for details of the prior medication that is permitted or prohibited according to the inclusion and exclusion criteria. The prohibited (prior) medications and devices listed in Section 6.6 are also prohibited during the study. The following medications are prohibited during the study:

- Drugs that have known bone marrow toxicities
- Potent CYP3A4 inhibitors (boceprevir, clarithromycin, conivaptan, elvitegravir/ritonavir, fluconazole, indinavir, itraconazole, ketoconazole, lopinavir/RIT, mibefradil, nefazodone, nelfinavir, posaconazole, ritonavir, saquinavir, telaprevir, telithromycin, tipranavir/ritonavir, troleandomycin, voriconazole)
- Potent CYP3A4 inducers (avasimibe, carbamazepine, enzalutamide, mitotane, nevirapine, phenobarbital, phenytoin, rifabutin, rifampin, rifapentine, St John's wort)
- Potent UGT1A9 inhibitors/inducers (UGT1A9 inhibitors/inducers include belumosudil, cannabidiol, cannabinol, deferasirox, diflunisal, eltrombopag, fosphenytoin/phenytoin, isavuconazole, medical cannabis, mefenamic acid, methylene blue, morniflumate, niflumic acid, perampanel, regorafenib, rifampicin, sorafenib, umifenovir)

Setanaxib is considered to be a weak inhibitor of CYP2C9, CYP2C19, and OAT3. Sensitive CYP2C9, CYP2C19 and OAT3 substrates, such as warfarin and phenytoin (CYP2C9), S-mephenytoin (CYP2C19), and acyclovir, cefaclor, ceftizoxime, famotidine, furosemide, methotrexate, oseltamivir carboxylate, and penicillin G (OAT3), should be used with caution when co-administered with setanaxib due to risk of increased drug concentrations. Setanaxib has potential induction effects on CYP2B6. Sensitive substrates of CYP2B6, such as tamoxifen, valproic acid, and cyclophosphamide should be used with caution due to risk of decreased drug concentration and reduced efficacy.

In addition, setanaxib inhibited BCRP and MDR1 (P-gp) in vitro. This may result in increased exposures of applicable concomitant medications, and hence caution should be exercised with use of sensitive BCRP and P-gp substrates, such as digoxin.

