single oral doses of setanaxib of up to 1800 mg and multiple oral doses of setanaxib of up to 900 mg daily for 10 days. A sixth Phase 1 study has recently also been performed, to evaluate higher multiple oral doses of setanaxib than previously assessed. A total of 46 healthy male and female subjects were enrolled and received single oral doses of setanaxib of up to 1600 mg (N=30) or multiple oral doses of setanaxib of up to 800 mg BID (total daily dose 1600 mg) for 10 days (N=32).

In the Phase 1 program, setanaxib has been generally well tolerated, with a low incidence of AEs. There have been no deaths, no SAEs, and no AE of severe intensity. Most were TEAEs and were mild and self-limiting and were considered not related to treatment by the investigator.

In a clinical study in patients with PBC (GSN000300), a total of 111 patients with PBC and inadequate response to UDCA were randomised in equal proportions to receive placebo, setanaxib 400 mg OD, or setanaxib 400 mg BID for 24 weeks. This dosing regimen was considered safe and well tolerated, and the treatment was pharmacologically active (based on observed dose-related improvements in liver enzymes); however, the observed clinical efficacy in the target patient population was considered insufficient, and a Phase 2b/3 clinical study in patients with PBC is planned in which doses of up to 800 mg BID for 52 weeks will be evaluated (GSN000350).

In this study in SCCHN, setanaxib 800 mg BID will be evaluated. This is the same as the proposed highest dose in the planned Phase 2b/3 study in PBC (GSN000350) and represents a two-fold increase compared to the highest dose evaluated in the previous study in patients with PBC (GSN000300), where there were no safety signals of concern. At this dose, the expected exposures will be around the defined no-observed-adverse-effect level (NOAEL) for both the parent (setanaxib) and metabolite (GKT138184); however, the NOAEL defining toxicology signals can be monitored in the clinical setting, and were not observed in either healthy volunteers at 800 mg BID for 10 days or patients at 400 mg BID for 24 weeks.

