- 13. Known human immunodeficiency virus (HIV) infection or acute or chronic hepatitis B or C infection. Patients with a past or resolved hepatitis B virus infection (defined as the presence of hepatitis B core antibody [HBcAb] and absence of hepatitis B surface antigen [HBsAg]) are eligible provided the hepatitis virus DNA test is negative.

Patients positive for hepatitis C antibody are eligible only if polymerase chain reaction (PCR) is negative for hepatitis C virus RNA. Patients with ongoing anti-viral therapy with potent inhibitors of CYP3A4 are not eligible. Testing for HIV is only required if clinically indicated and is not mandatory for this study.

- 14. Serious chronic gastrointestinal conditions associated with diarrhoea.
- 15. History of significant haematological problems, such as blood dyscrasias requiring treatment, aplastic anaemia, myelodysplastic syndrome, or leukaemia.
- 16. Surgery (eg, stomach bypass) or medical condition that might significantly affect absorption of medicines (as judged by the investigator).
- 17. A positive pregnancy test or breastfeeding for female patients.
- 18. Evidence of any of the following cardiac conduction abnormalities: a QTc Fredericia interval >450 milliseconds for male patients or >470 milliseconds for female patients. Patients with a second- or third-degree atrioventricular block are to be excluded.
- 19. TSH >ULN at Screening.
- 20. Unstable cardiovascular disease as defined by any of the following:
 - a. Unstable angina within 6 months prior to Screening
 - b. Myocardial infarction, coronary artery bypass graft surgery, or coronary angioplasty within 6 months prior to Screening
 - c. Cerebrovascular accident within 6 months prior to Screening
 - d. New York Heart Association Class III or IV heart failure
- 21. Presence of any laboratory abnormality or condition that, in the opinion of the investigator, could interfere with or compromise a patient's treatment, assessment, or compliance with the protocol and/or study procedures.
- 22. Any other condition that, in the opinion of the investigator, constitutes a risk or contraindication for the participation of the patient in the study, or that could interfere with the study objectives, conduct, or evaluation.
- 23. Use of medications known to be potent CYP3A4 inhibitors or inducers, or potent uridine diphosphate (UDP)-glucuronosyltransferase 1A9 (UGT1A9) inhibitors or inducers, within 21 days prior to IMP administration.

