4.3.1 Premature Discontinuation of Investigational Medicinal Product

Patients should discontinue the IMP if any of the following occurs:

- 1. The patient withdraws his/her consent to participate in the study.
- 2. The patient develops an illness that would interfere with his/her continued participation in the study, at the investigator's discretion.
- 3. The patient is noncompliant with study procedures or medication, that in the opinion of the investigator, impacts patient safety and/or the integrity of the study results.
- 4. The patient takes a prohibited medication that warrants the IMP discontinuation at the discretion of the investigator (see Section 6.7).
- 5. The patient is confirmed to be pregnant.
- 6. The sponsor or regulatory agency requests withdrawal of the patient.

- 7. The patient is withdrawn for safety reason per the investigator's judgment.
- 8. IMP rechallenge results in anaemia or hypothyroidism IMP interruption criteria being met again (see Section 6.4.2).

At the time of premature IMP discontinuation, the patient should complete the assessments indicated at the EoT Visit (see Table 1). The patient will also be required to attend a Safety Follow-up Visit at 28 days after the last IMP dose. In addition, patients who discontinue study treatment prior to radiological progression will continue to be followed for tumour assessments until RECIST v1.1-defined disease progression, and for survival.

Patients who withdraw consent should be asked whether they would still allow contact for determination of survival follow-up. If patients consent to survival follow-up, they will be withdrawn from study treatment and other study procedures but are not considered to have withdrawn from the study.

Patients who discontinue IMP prematurely will not be replaced.

For details of permitted IMP dechallenge and rechallenge, see Section 6.4.2.

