Appendix III contains a list of common medications that should be avoided or used with caution.

Regarding Covid-19 vaccination, as setanaxib does not have immunosuppressive properties based on nonclinical and clinical safety data, and as the available literature and expert assessment concludes that patients taking pembrolizumab and other immune checkpoint inhibitors should be considered for Covid-19 vaccination, the sponsor considers that study patients may undergo Covid-19 vaccination during the study. All approved Covid-19 vaccines are allowed in setanaxib studies and are to be recorded as a concomitant medication. It is important that the Covid-19 vaccinations are not delayed.

If patients receive a prohibited medication, investigators should consider whether IMP administration should be temporarily interrupted or permanently discontinued. Additionally, if a patient has taken a prohibited medication (eg, short-term antifungal therapy) and the investigator learns about it later, this might not lead to the permanent discontinuation of IMP.

All medication (including vaccines, over-the-counter or prescription medicines, vitamins, and/or herbal supplements) taken from 3 months (90 days) before Screening Visit until the end of the Safety/Efficacy Follow-up Period will be recorded in the appropriate section of the eCRF.

The following details must be recorded in the eCRF:

- Medication name, ideally the generic and/or brand names
- Reason for use
- Start and end date of administration
- The dose, route and frequency of administration

The medical monitor should be contacted if there are any questions regarding prior or concomitant medication or procedures.

For patients who discontinued study treatment but remain followed for tumour assessment until RECIST v1.1-defined disease progression, any further anti-cancer medication will be recorded until progression.

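### Protocol Section 6.8 prohibits phenytoin and then names it for cautious use; in Appendix III five drugs marked Avoid are also listed for caution, and no rule says which list governs

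*Protocol*

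**What the plan says.** Section 6.8 opens with drugs that may not be taken during the study. Phenytoin is in the bullet "Potent CYP3A4 inducers (avasimibe, carbamazepine, enzalutamide, mitotane, nevirapine, phenobarbital, phenytoin" and appears again in the UGT1A9 bullet: "fosphenytoin/phenytoin, isavuconazole, medical cannabis". The paragraph after the bullets turns to drugs whose own levels setanaxib may change. It asks for caution when setanaxib is given with sensitive CYP2C9 substrates, "such as warfarin and phenytoin (CYP2C9".

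Later in Section 6.8 the reader is sent to Appendix III for drugs to avoid or use with caution. Table 6 there is the Avoid list. Table 5 (QT risk) and Table 7 (sensitive substrates) are caution lists.

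Section 6.8 also states what follows when a prohibited drug is taken: "If patients receive a prohibited medication, investigators should consider whether IMP administration should be temporarily interrupted or permanently discontinued". It refers questions about medication to the medical monitor. SAP Section 10.6 adds that the sponsor will review all medications by hand throughout the study and flag those prohibited under protocol Section 6.8.

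**The concern.** Prohibition and cautious co-administration are different instructions, and for phenytoin both stand in the same section. The Appendix III tables work as a look-up: Tables 6 and 7 have a usage column and Table 5 carries its instruction in the title. A coordinator who finds voriconazole in Table 7 reads Caution, and nothing there points to Table 6.

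Patients already on these drugs should not enter, because exclusion criterion 23 bars "Use of medications known to be potent CYP3A4 inhibitors or inducers" within 21 days before IMP. The realistic risk is therefore a new prescription during the study. The protocol's own example of a prohibited drug being taken is of this kind: "if a patient has taken a prohibited medication (eg, short-term antifungal therapy". A site that treats the drug as a caution drug would start it alongside setanaxib and would have no reason to consider interrupting IMP.

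Per Table 6, three of the five drugs would raise setanaxib exposure and two would lower it. The upward direction matters because, by the dose rationale in Section 3.2, "the expected exposures will be around the defined no-observed-adverse-effect level (NOAEL".

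**Working it through.** The plan has no figure of its own on this point, so the check compares the lists and then looks at the exposure margin.

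**1. Drugs prohibited by name that also have a caution entry**

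| Drug | Section 6.8 prohibition | Table 6: usage, IMP exposure | Caution entry |
|---|---|---|---|
| Phenytoin | Potent CYP3A4 inducer; also in UGT1A9 list | Avoid, decreased | Section 6.8 (CYP2C9); Table 7 (CYP2C9, CYP2B6) |
| Carbamazepine | Potent CYP3A4 inducer | Avoid, decreased | Table 7 (CYP2B6) |
| Voriconazole | Potent CYP3A4 inhibitor | Avoid, increased | Table 7 (CYP2C19) |
| Clarithromycin | Potent CYP3A4 inhibitor | Avoid, increased | Table 5 (QT) |
| Fluconazole | Potent CYP3A4 inhibitor | Avoid, increased | Table 5 (QT) |

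By list, the overlap is 1 of the 15 drugs named in the Section 6.8 caution paragraphs, 3 of the 30 in Table 7 and 2 of the 65 in Table 5. Phenytoin is already among the 3 in Table 7, so the distinct total is 3 + 2 = 5: three inhibitors and two inducers.

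**2. Drugs caught by a class.** Name matching misses class prohibitions. Section 6.8 prohibits drugs with known bone marrow toxicity and carries forward the Section 6.6 prohibitions, which include chemotherapy. Its caution paragraph nevertheless names methotrexate and cyclophosphamide, and so does Table 7. The protocol does not assign individual drugs to these classes, so placing the two there rests on ordinary pharmacology. Five is thus a count of drugs prohibited by name and not of every overlap.

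**3. Search for a rule on which list governs.** Exclusion 23, Sections 6.6 and 6.8, and Appendix III with its introduction contain none. The nearest text is the referral of questions to the medical monitor, which sets no order between lists.

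**4. Room for higher exposure.** In Table 3, margin = exposure at the dog NOAEL ÷ human exposure at 800 mg BID. For Week 39 AUC:
- Setanaxib: 195.5 / 193 = 1.01 (printed 1.0).
- GKT138184: 27.0 / 38.2 = 0.71 (printed 0.7).
- Combined: 222.5 / 231.2 = 0.96 (printed 1.0).

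If an inhibitor multiplied setanaxib AUC by a factor f, the parent margin would become 1.01 / f, which is below 1 for nearly any f above 1. The documents give no value of f for any of the three inhibitors. Table 6 does not say how the metabolite would move.

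**The case against.** The strongest reply is that the intent is not in doubt. Section 6.8 is categorical. Exclusion 23, Section 6.6, the drug-interaction row of Table 2 and Appendix III Tables 4 and 6 all point the same way, and the antifungal example treats such use as prohibited. The lists also answer different questions: Table 6 concerns what the drug does to setanaxib, Table 7 what setanaxib does to the drug, and Table 5 QT risk. A caution entry in one does not lift a prohibition in another. This stands as an account of how the overlap arose and which status was meant. It does not cure the Section 6.8 sentence, which presupposes that phenytoin is being co-administered, and it does not help a site that consults one table only.

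Two safeguards also count. The SAP Section 10.6 review is keyed to the Section 6.8 list, which names all five drugs, so detection does not depend on how the site reads the tables. The medical monitor is available for questions. Both limit the harm. But the review may come after the drug is started, and a site that sees no conflict has no question to ask.

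Three smaller replies also stand:
- The UGT1A9 entry is the weaker prohibition of phenytoin, because the bullet is headed potent while its bracketed list drops that word. The CYP3A4 entry is the unambiguous one.
- The dose rationale goes on to say that the NOAEL-defining signals can be monitored clinically and were not seen at 800 mg BID for 10 days or 400 mg BID for 24 weeks.
- The exposure argument applies to the three inhibitors only. For the two inducers the concern is weaker treatment.

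**Conclusion.** The point holds as a minor safety-conduct error that is wrong as written. For phenytoin the conflict lies within Section 6.8. For all five drugs it lies between Table 6 and a caution table. Some further caution drugs fall under class prohibitions.

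A reader might infer more than the documents support:
- *That the protocol permits these drugs.* It does not; the intended status is prohibited, and only the statement of precedence is missing.
- *That misuse would go unnoticed.* The sponsor's medication review is designed to pick it up, though possibly late.
- *That patients would come to measurable harm.* The documents give neither the change in setanaxib exposure nor the number of patients likely to start one of these drugs, so no size can be put on it.
- *That the efficacy analysis is compromised.* No sample-size, power, alpha or estimand figure depends on this text.

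The conclusion rests on protocol v4.0 (25 April 2023). SAP Section 6.0 cites v5.0 (12 December 2023), which was not available for this review.

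**What to change.** First check whether protocol v5.0 still contains the overlap. If it does:

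1. Delete phenytoin from the caution sentence in Section 6.8.
2. Add one sentence to both Section 6.8 and Appendix III: *Where a drug appears in more than one list, or belongs to a prohibited class, the prohibited/Avoid status prevails.* This settles all five named drugs and also methotrexate and cyclophosphamide.

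Keep the Table 5 and Table 7 entries. They carry true interaction information that is useful after an inadvertent exposure, and Table 5 comes from an outside list.

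As a separate clerical correction, Section 4.3.1 item 4 reads "The patient takes a prohibited medication that warrants the IMP discontinuation at the discretion of the investigator (see Section 6.7". Section 6.7 covers pembrolizumab background treatment and holds no list of prohibited drugs; the reference should be to Section 6.8.

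The cost is one deletion, one sentence in two places and one corrected cross-reference. Design and analysis are unchanged.
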